2.2 STUDY OBJECTIVES

Primary Objective:

To investigate the safety and tolerability of ascending subcutaneous weekly doses of NNC0361-0041 plasmid in patients with T1D.

Secondary Objectives:

To investigate effect on target engagement, immune response, and beta cell function following ascending subcutaneous weekly doses of NNC0361-0041 plasmid in patients with T1D.

3. Population Definitions

Up to 12 patients will be randomized to treatment vs. placebo within each of 4 cohorts. The goal is to have a minimum of 9 patients within each cohort to have received at least 10 of the planned 12 treatment doses.

Randomized:	Met eligibility criteria and randomly assigned to a treatment arm without consideration of actually receiving
	treatment.
Randomized and partially	Met eligibility criteria, randomly assigned to a treatment
treated:	arm and received at least 1 – 9 doses.
Randomized and treated:	Met eligibility criteria, randomly assigned to a treatment
	arm and received at least 10 doses.
Pretreatment period	From signing of informed consent until 1 st treatment

On-treatment period	From 1 st treatment through visit 15 (or 5 weeks after last treatment for subjects not receiving all injections)
Follow-up period	From visit 15 (or 5 weeks after last treatment) through visit 17

Up to 2 additional individuals within each cohort may be enrolled to complete the target 9 patients randomized and treated to account for those who are randomized and partially treated.

4. SAFETY and INSULIN SECRETION ANALYSES

4.1 SAFETY

Clinical data (vital signs, AEs) from the first 48 hours for the first two patients enrolled within a cohort (sentinel cases) will be evaluated by the TrialNet Medical Monitor and the Novo Nordisk Safety group to assess whether accrual within the cohort can continue. A safety analysis to support the decision to proceed to the next dose level will be conducted when at least 9 patients have received the first four injections and have had 4-week assessments (visit 6.) This analysis is conducted by TrialNet DMC and the NovoNordisk Safety group and will include cumulative data from previous cohorts when available.

4.2 INSULIN SECRETION ANALYSIS

The insulin secretion analysis is conducted when all subjects have completed their final visits through visit 17 (1 year after first treatment).

5 ANALYSIS SETS

5.1 FULL ANALYSIS POPULATION

The full analysis (FA) population will include all patients who are randomized with study drug assignment designated according to the initial randomization. In exceptional cases subjects from the FA may be excluded. In such cases the exclusion will be justified and documented. The subjects in the FA will contribute to the analyses 'as treated'.

5.2 SAFETY ANALYSIS POPULATION

The safety analysis (SA) population will include all randomized patients who receive at least one dose of study medication, with treatment assignments designated according to actual study medication received. The SA population will be the primary population for safety and treatment evaluations.

5.3 EVALUABLE POPULATION FOR PHARMACOKINETICS

The PK concentration population is defined as all patients in the SA population who have at least one dose.

5.4 ANALYSIS SUBGROUPS

Of particular interest for safety outcomes and potential worsening of insulin secretion is the subset of the safety analysis population who receive at least 10 doses of their assigned treatment (FA10). Those not included in FA10 will also be analyzed as a separate subgroup. AEs reported through 4 weeks (visit 6) will also be a defined subgroup for safety assessments.

5.5 TREATMENT MISALLOCATIONS

Patients who were randomized but not treated with study medication will be reported under their randomized treatment group (FA). However, they are by definition excluded from the safety analyses.

Patients who were randomized but received incorrect treatment, will be reported under their randomized treatment group (FA) but will be reported under the treatment they actually received (SA) for all safety analyses and treatment evaluations.

5.6 PROTOCOL DEVIATIONS

All deviations will be described when they appear and relate to the statistical analyses or analyses sets. No patients will be excluded from primary analyses based on eligibility evaluations.

6 ENDPOINTS AND COVARIATES

6.1 SAFETY ENDPOINTS

The primary endpoint is the number of adverse events recorded during the on-treatment period through visit 15. No formal statistical analysis will be made for the primary outcome. The primary endpoint will be presented by treatment groups in a summary table including number of AEs, number of subjects with at least 1 AE and percentage of exposed subjects with at least 1 AE. Placebo will be pooled across cohorts for comparison. AEs will also be summarized by system organ class, preferred term, seriousness, severity, outcome, and relationship to IMP using descriptive statistics.

Adverse events will be summarized over the entire trial (i.e., on-treatment and follow-up period). (i.e., visit 0 through visit 17 at 12 months). They will be further summarized by whether they occurred up to and including visit 6 (4 weeks) or later. Follow-up visits 16 and 17 will be conducted to obtain 6- and 12-month data on participants' metabolic status and reportable adverse event assessments.

All AEs will be coded using the CTCAE and mapped to latest version of Medical Dictionary for Regulatory Activities (MedDRA). AEs will be summarized by system organ class, preferred term, seriousness, severity, outcome, and relationship to IMP using descriptive statistics.

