#### 4.4 Overview of Treatments Administered

The plasmid NNC0361-0041 to be used in this first in human trial is supplied in a 9 mg/ml stock solution and will be prepared as an injection for subcutaneous administration. As described in section 4.4.2 below, the injections will be prepared according to the dose specified for each cohort, beginning with a 1-mg dose in cohort 1 and ending with a final dose of 25 mg in cohort 4 for this trial. The placebo will be administered in the same volume as the treatment. Doses will be administered on a weekly basis for 12 consecutive weeks.

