### 4.4.2 Dosing and Dose Withholding Criteria

Dosing is dependent on the current cohort open to participant enrollment. Table 1 below demonstrates the dose to be administer in each cohort. No routine premedication is needed prior to each subcutaneous injection of the study drug.

Table 1: Planned Dosing Levels of Plasmid NNC0361-0041 or Placebo

Cohort	Dose (mg)	Escalation factor	IP volume (mL) (9mg/mL stock solution)	Injection(s) (mL)
1	1	-	0.11	0.11
2	5	5	0.56	0.56
3	12.5	2.5	1.4	0.7 + 0.7
4	25	2	2.8	0.94 + 0.94 + 0.94

Administration of injections will be withheld based on the following criteria:

- 1. Individuals with fever: Temperature greater than 38.5 °C (101.3 °F) within 48 hours of each dose
- 2. Individuals with evidence of active infection at time of dosing.

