#### 4.9.2 Between Cohorts: Evaluation of accumulated data

The TrialNet Medical Monitor and Novo Nordisk Trial Safety Group will review accumulated data after 9 individuals within a cohort have data available from visit 6 *masked to treatment assignment* and have received the first 5 scheduled doses. This data includes insulin dose, all available MMTT AUC C-peptide values, AE reports regardless of relationship to study drug, vital signs, as well as clinical laboratory data. Clinical laboratory data including normal ranges and C-peptide will be provided by individual participant as well as in summary form.

The DSMB will review the same interim data. Data from placebo participants regardless of cohort will be grouped together.

Dose escalation to the next cohort will require an absence of any of the rules for interruption of the trial/cessation of study (section 4.10) and concurrence by both the DSMB and Novo Nordisk Trial Safety Group.

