# 8 STATISTICAL CONSIDERATIONS AND ANALYSIS PLAN).

The primary objective of this study is to investigate the safety and tolerability of ascending subcutaneous weekly doses of NNC0361-0041 plasmid in patients with T1D. Secondary objectives are to investigate effect on target engagement, immune response, and beta cell function following ascending subcutaneous weekly doses of NNC0361-0041 plasmid in patients with T1D.

Up to 12 patients will be randomized to treatment vs. placebo within each of the 4 cohorts. The goal is to have a minimum of 9 patients within each cohort to have received at least 10 of the planned 12 treatment doses.

The following groups and periods are defined for analytic purposes:

Randomized:	Met eligibility criteria and randomly assigned to a treatment arm without consideration of actually receiving treatment.
Randomized and partially treated:	Met eligibility criteria, randomly assigned to a treatment arm and received at least 1 – 9 doses.
Randomized and treated:	Met eligibility criteria, randomly assigned to a treatment arm and received at least 10 doses.
Pretreatment period	From signing of informed consent until 1st treatment
On-treatment period	From 1 st treatment through visit 15 (or 5 weeks after last treatment for subjects not receiving all injections)
Follow-up period	From visit 15 (or 5 weeks after last treatment) through visit 17

Up to 2 additional individuals within each cohort may be enrolled to complete the target 9 patients randomized and treated to account for those who are randomized and partially treated for any

reason, including COVID-19 vaccination. Additional individuals may be enrolled upon agreement between TrialNet and Novo Nordisk

All randomized subjects will be used for analyses of PK endpoints and all subjects receiving at least one dose of randomized treatment (partially treated and treated combined) will be used for analyses of the primary endpoint. Subjects receiving placebo treatment will be pooled across cohorts.

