2.1 STUDY DESIGN

This is a placebo-controlled, double-blinded within cohorts, randomized, multiple ascending dose trial with a staggered trial design. A total of 48 patients with T1D are planned to be studied in 4 cohorts of 12 patients (9 on active and 3 on placebo treatment). Patients will be randomized in a 3:1 fashion within each cohort to receive recombinant supercoiled plasmid NNC0361-0041 or placebo. The randomization is not stratified. A centralized random permuted block design will be used to balance treatment assignments within cohorts.

Each treatment is defined as 12 weekly doses. Should it not be possible to administer all 12 doses, patients will be followed, nonetheless, for 12 months according to the protocol Schedule of Assessments.

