8.2.2 SAFETY ANALYSES

Safety data will be analyzed in the SA population. Adverse events and select laboratory values (e.g., hematology, blood chemistry and others) may also be summarized by the treatment arms. Only grade 2 or higher AEs are to be reported for visits 16 and 17, as per protocol.

On-Treatment Adverse Events

An overall summary of AEs as described above will be provided. AEs will be summarized for all doses and also by dose. The most commonly reported AEs (5% or more of patients) will also be summarized by preferred term. A summary of AEs by preferred term and maximum CTCAE grade, as well the grouped maximum CTCAE grade group (Grade 1-2 vs. Grade 3-4 vs. Grade 5) will be presented. Only patients who experience AEs during the AE reporting period will be listed.

Treatment Related Adverse Events

Treatment-related AEs are those judged by the Investigator to be at least possibly related to the study drugs [with a cause related to study drug as indicated on the case report form (CRF)] or for which relatedness is recorded as "unknown" by the Investigator. Similar summaries as noted for AEs will be provided for treatment related AEs.

Serious Adverse Events and Death

On-treatment SAEs and treatment-related SAEs will be summarized by MedDRA SOC and preferred term. Patients who experienced a SAE during the SAE reporting period will be listed for all randomized patients. The number and percentage of patients who experienced any serious treatment - emergent SAE will be summarized for all doses. A summary of SAEs by preferred term, maximum CTCAE grade and grade group will be presented.

Deaths will be summarized by time period (on-treatment vs. during follow-up) and cause of death. Deaths that occurred on or after first dose of study medication and within 28 days after the last dose of study medication are defined as on-treatment deaths. A listing of death data will also be provided and it will include all deaths that occurred during the reporting period for deaths which starts from the signing of the informed consent to the end of the follow up period for death.

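### For injection-site reactions, placebo pooled across cohorts matches no dose cohort on injection number or volume, so a by-cohort placebo display should sit beside it

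*SAP*

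**What the plan says.** Both documents pool placebo for the adverse event comparison. SAP 6.1 says "Placebo will be pooled across cohorts for comparison", and protocol section 8 says "Subjects receiving placebo treatment will be pooled across cohorts". For the DSMB's review between cohorts, protocol 4.9.2 says "Data from placebo participants regardless of cohort will be grouped together".

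Placebo exposure nevertheless depends on cohort. Protocol 4.4 says "The placebo will be administered in the same volume as the treatment". The volumes and their division into injections are in the table headed "Table 1: Planned Dosing Levels of Plasmid NNC0361-0041 or Placebo": a single injection in cohorts 1 and 2, two in cohort 3, and "0.94 + 0.94 + 0.94" mL in cohort 4.

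Allocation is made within cohort. SAP 2.1 says "A centralized random permuted block design will be used to balance treatment assignments within cohorts", with 9 active and 3 placebo planned in each.

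SAP 8.2.2 adds "AEs will be summarized for all doses and also by dose". It does not say whether this means dose level, or whether placebo would be split. The SAP plans no separate summary of injection-site reactions, although protocol 7.2 gives them their own section of the case report form.

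**The concern.** A placebo column is useful for a local reaction if it shows what the same injections would have done without the plasmid. Here dose and injection burden rise together: cohort 4 has the highest dose and also the most injections and the largest volume. Set against a pooled column with an intermediate burden, an excess in cohort 4 could come from the plasmid or from the extra injections. A real local effect in cohorts 1 and 2 could be hidden, because those cohorts have a lighter burden than the pool.

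This matters because the trial is first-in-human, its primary endpoint is the number of AEs, and protocol 6.2.2 names injection-site reactions as a potential risk to be checked at every visit. Within-cohort randomization provides a volume-matched control. The planned AE display does not use it, whereas SAP 8.2.3 compares C-peptide both within cohort (3 v 9) and against pooled placebo (12 v 9).

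**Working it through.** **Inputs.** Doses of 1, 5, 12.5 and 25 mg, the 9 mg/mL stock and the injection splits come from protocol Table 1. The 9 active and 3 placebo per cohort, and the 12 weekly doses, come from SAP 2.1. The number of placebo injections is inferred from the same-volume sentence and the title of Table 1; nothing in the documents contradicts it.

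**Table 1 reproduced.** Dose ÷ 9 gives 0.111, 0.556, 1.389 and 2.778 mL. Table 1 rounds these to 0.11, 0.56, 1.4 and 2.8 (3 × 0.94 = 2.82).

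**Pooled placebo exposure per visit, 3 participants from each cohort.**
- Injections: (1 + 1 + 2 + 3) ÷ 4 = 1.75
- Volume: (0.11 + 0.56 + 1.4 + 2.8) ÷ 4 = 1.2175 mL

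**Ratio of active to pooled placebo with no plasmid effect.** The documents give neither a reaction rate nor a risk pattern, so every row below is an assumption. All 12 doses are taken as given. For event counts proportional to injection number, the ratio is k ÷ 1.75, where k is injections per visit. For the percentage with at least one event, each participant's risk is 1 − (1 − p)^(12k), with p the risk per injection and injections independent. Pooled placebo is the mean of the four cohort values.

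| Assumption | Cohort 1 | Cohort 2 | Cohort 3 | Cohort 4 |
|---|---|---|---|---|
| Risk per visit, whatever the number of injections | 1.0 | 1.0 | 1.0 | 1.0 |
| Event counts, proportional to number | 0.57 | 0.57 | 1.14 | 1.71 |
| Percentage with an event, p = 2% | 0.65 | 0.65 | 1.15 | 1.55 |
| Percentage with an event, p = 5% | 0.74 | 0.74 | 1.15 | 1.36 |
| Percentage with an event, p = 10% | 0.86 | 0.86 | 1.10 | 1.17 |

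At p = 2% the underlying percentages are 21.5, 21.5, 38.4 and 51.7, against 33.3 for pooled placebo.

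**DSMB reviews between cohorts, taking 3 placebo participants per cohort to date.**
- After cohort 1: matched on number and volume.
- After cohort 2: matched on number (1 v 1) but not volume (0.56 v 0.335 mL, ratio 1.67).
- After cohort 3: matched on neither (2 v 1.33 injections, ratio 1.50; 1.4 v 0.69 mL, ratio 2.03).

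**Precision.** With no events, the exact two-sided 95% upper limit is 1 − 0.025^(1/n): 70.8% for 0/3 and 26.5% for 0/12. At p = 2%, expected events are participants × 12 × k × 0.02: active 2.16, 2.16, 4.32 and 6.48; placebo by cohort 0.72, 0.72, 1.44 and 2.16; pooled placebo 5.04. A rough 95% factor either way on the rate ratio is exp(1.96 × √(1/a + 1/b)), with a and b the expected active and placebo events:

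| Cohort | Against pooled placebo | Against same-cohort placebo |
|---|---|---|
| 1 and 2 | 4.9 | 14.4 |
| 4 | 3.2 | 4.7 |

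The formula is crude at counts this small, and it treats events as independent. Repeat reactions in one participant would widen every figure.

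**The case against.** The strongest reply is that this is a preference about display. Pooling is stated consistently in both documents, SAP 6.1 rules out a formal analysis of the primary outcome, and the size of any distortion is assumed. It also lies within noise: around 1.71, the pooled cohort 4 interval runs from about 0.53 (1.71 ÷ 3.2) to about 5.5 (1.71 × 3.2). The matched rows are less precise still, most of all in cohorts 1 and 2, and a reader can over-read 0/3 as easily as a pooled column. All of this stands. It limits the point to an inexpensive improvement and is why the pooled column should stay. It does not make that column a matched comparator. The imprecision of 0/3 is visible on the page; the mismatch inside a pooled column is not.

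A reader might infer that dose escalation is exposed. The documents do not support that. The triggers in protocol 4.10 use seriousness, grade and relatedness, with no placebo ratio. The Novo Nordisk Trial Safety Group reviews masked data and must concur. Injection-site data are reviewed within cohort at the sentinel steps (protocol section 6). The DSMB sees grouped placebo, but also events graded and assessed for causality.

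A reader might also point to risk proportional to total volume, which gives 0.09, 0.46, 1.15 and 2.30. No passage supports that pattern, so these figures should not be taken as the likely size.

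Finally, the by-dose summary in SAP 8.2.2 may already allow a view by dose level. It neither commits to one for placebo nor excludes it.

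**Conclusion.** The mismatch in exposure is certain, given that placebo follows Table 1. Whether it distorts anything depends on how local reactions relate to injection number or volume, on which the documents are silent; no bias is a possible answer. If risk is proportional to number, cohorts 1 and 2 would look better than pooled placebo and cohort 4 worse, with no plasmid effect at all. The 0.57 to 1.71 range applies to event counts only. The percentage with at least one reaction moves less, and less still as reactions become common.

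The consequence is confined to reading local tolerability by dose in a descriptive table. It would be wrong to conclude that pooling is an error for systemic AEs, that the primary endpoint is invalid, or that within-cohort rows of 9 v 3 could support a test. This is an optional improvement. Confidence is high in the mismatch, and there is no basis for a claim about the size of any misleading result.

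**What to change.** Keep pooled placebo for the primary and systemic AE tables. Add to SAP 6.1 and 8.2.2:

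> For injection-site reactions, as captured on the dedicated CRF section, active and placebo will also be shown side by side by cohort (planned 9 v 3), beside the pooled placebo column, as number of events and number and percentage of participants with at least one event. This display is descriptive.

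Using the CRF section to define the events avoids a loose category of local AEs, which the SAP does not define and which could not be programmed consistently. Splitting by cohort matches injection number and volume together. It would also help to state whether the by-dose summary in SAP 8.2.2 means dose level and whether it splits placebo.

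The cost is one extra table from data already collected; sample size, tests and decision rules do not change. The drawback is the precision shown above, with 3 placebo participants per row and under one expected placebo event in each of cohorts 1 and 2 at the assumed 2%. The table should say that it supplements the pooled column and supports no test.

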6.2 SECONDARY ENDPOINTS

 $\Delta AUC_{0-2h,C-peptide,MMTT}$; Relative change in the area under the plasma C-peptide concentration-time curve from time 0 to 2 hours during MMTT from baseline to 3 months (visit 14) between groups. The comparison will be blinded until the last patient has been followed for 12 months.

Additional Outcomes and Analyses

It is the aim to perform additional analysis to get information of the appearance and disappearance of Plasmid DNA and RNA at various time points during the trials conduct period:

- Plasmid DNA and RNA concentrations at selected time points before and from 1 hour to up to 48 hours after the first dose (Visits 0-2, days 0-2)
- Plasmid DNA and RNA concentrations before second dose (Visit 3, day 7 +/- 1 day)
- Plasmid DNA and RNA concentrations before dose 5 (Visit 6, day 28 +/- 1 day)
- Plasmid DNA and RNA concentrations before dose 8 (Visit 9, day 49 +/- 1 day)

• Plasmid DNA and RNA concentrations at selected time points after last dose (Visit 14, day 84 +/- 3 days; Visit 15, day 120 +/- 14 days; Visit 16, day 180 +/- 14 days; and Visit 17, day 365 +/- 14 days)

Additional analysis of the impact of study drug on metabolic outcomes (Section 5.4) will be determined at 1-, 3-, 6-, and 12-months following treatment including analysis of changes of these parameters from baseline.

Target Engagement, Mechanistic Outcomes and Exploratory Analysis

The primary time period for evaluation of target engagement and mechanistic outcomes will be accumulated data through visit #14.

The mechanistic hypothesis underlying this therapy is that NNC0361-0041 is a tolerizing agent (cross reference to protocol section 2.2.2). Due to the low number of transfected cells, it may not be possible to detect any systemic effect. However, evidence supporting this hypothesis would be the detection of plasmid-derived mRNA in the circulation or increase in certain cytokines. Further supporting this hypothesis, will be the demonstration of a change in number (frequency), or change of phenotype in circulating immune cells from baseline. These studies will include, but are not limited to, flow cytometry, measures of gene expression, and cytokine detection. The relationships of such measures will be evaluated with respect to C-peptide, insulin dose, glycemic control, PK and PD markers of therapy, and genotype (including, but not limited to coding and non-coding genes HLA, insulin-VNTR, CD25, PTPN2, and IL10). Additional exploratory analysis for target engagement and mechanistic outcomes to assess the duration of such effects will be done using data through month 12 post-dosing.

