#### Autoantigen (Pre-proinsulin)

Rationale: The goal is use host machinery to express ectopic transgenes and facilitate the presentation of PPI peptides in the context of MHC class I and II molecules to host T cells via endogenous antigen processing and presentation machinery. The hypothesis is that both CD4+ and CD8+ T cell responses will be impacted, with the net effect of shifting the balance to favor immune regulation. Potential side-effects may include a delayed hypersensitivity reaction at the injection site or in any site the drug and transgene may ultimately be expressed. While the expectation is that endogenous Tregs will be induced in response to the drug, mechanistic and clinical data will also monitor the potential for the transgene to induce the expansion and/or activation of effector cells that might accelerate beta cell loss.

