#### 8.4 Target Engagement, Mechanistic Outcomes and Exploratory Analysis

The primary time period for evaluation of target engagement and mechanistic outcomes will be accumulated data through visit #14.

The mechanistic hypothesis underlying this therapy is that NNC0361-0041 is a tolerizing agent (see section 2.2.2). Due to the low number of transfected cells it may not be possible to detect any systemic effect. However, evidence supporting this hypothesis would be the detection of plasmid derived mRNA in the circulation or increase in certain cytokines. Further supporting this hypothesis will be the demonstration of a reduction in number (frequency), or change of phenotype, or function of antigen specific autoreactive T cells towards regulation. These studies will include, but not be limited to flow cytometry, measures of gene function, and evaluation of cytokine levels. The relationships of such measures will be evaluated with respect to C-peptide, insulin dose, glycemic control, PK and PD markers of therapy, and genotype (including, but not limited to coding and non-coding genes HLA, insulin-VNTR, CD25, PTPN2, and IL10). Additional exploratory analysis for target engagement and mechanistic outcomes to assess the duration of such effects will be done using data through month 12 post dosing.

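### SAP 6.2 drops the direction and the cell population from the protocol's criterion for further support of tolerance, so a rise in effector cells would literally count as support

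*SAP*

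**What the plan says.** Both documents start from the same hypothesis. In the SAP's words: "The mechanistic hypothesis underlying this therapy is that NNC0361-0041 is a tolerizing agent". Both give the same first tier of evidence; the SAP version is that "evidence supporting this hypothesis would be the detection of plasmid-derived mRNA in the circulation or increase in certain cytokines". They part on the second tier.

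- Protocol 8.4 looks for "the demonstration of a reduction in number (frequency), or change of phenotype, or function of antigen specific autoreactive T cells towards regulation".
- SAP 6.2 says the further support "will be the demonstration of a change in number (frequency), or change of phenotype in circulating immune cells from baseline".

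Protocol 6.1.3, in the paragraph on the autoantigen, gives the direction that the product is meant to produce: CD4+ and CD8+ T-cell responses are to be affected "with the net effect of shifting the balance to favor immune regulation". The same paragraph gives the mechanistic data, together with the clinical data, a second task: to "monitor the potential for the transgene to induce the expansion and/or activation of effector cells that might accelerate beta cell loss".

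SAP 2.2 lists target engagement and immune response among the secondary objectives. Protocol 5.3 classes the mechanistic assays as exploratory. SAP section 2 describes the SAP as a supplement to the protocol. SAP section 1 records that this is an updated version but gives no reason for the different wording.

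**The concern.** A criterion for support should separate the hypothesis from its opposite. The protocol's second-tier criterion does so: it names the cells that matter and the way they should move. The SAP's version can be met by movement either way, in any circulating immune cell. The opposite here is a risk the protocol itself raises, namely that the transgene drives effector cells and speeds beta-cell loss. A report written to the SAP wording could list such a finding as support for tolerance.

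Naming baseline as the only reference adds a second weakness. Immune measures can move for reasons unrelated to the drug. Protocol 6.3.1.2 acknowledges that COVID-19 vaccination may affect the study's immune measures, and inclusion criterion 17 allows vaccination to be completed as little as two weeks before randomization. A baseline taken then may not be stable, and a later movement shared by active and placebo participants would still be a change from baseline.

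At stake is the mechanistic conclusion on target engagement and immune response, not the safety conclusion.

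**Working it through.** The plan states no figure on this point, so there is none to reproduce. The check is a comparison of the two texts.

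**Step 1: the criteria element by element.**

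| Element | Protocol 8.4 | SAP 6.2 | Effect of the SAP wording |
|---|---|---|---|
| Direction | Fewer cells, or a shift towards regulation | None | Looser |
| Cells | Antigen-specific autoreactive T cells | Any circulating immune cells | Looser |
| Function | Counts | Not listed | Narrower |
| Reference | None named | Baseline | Neither names placebo |
| First-tier evidence | Plasmid mRNA or cytokine increase | Same | Unchanged |

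No other part of the SAP restores direction or population. SAP 8.1.1 gives only general descriptive statistics for continuous data.

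**Step 2: hypothetical findings under each criterion, read literally.**

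| Finding | Protocol 8.4 | SAP 6.2 |
|---|---|---|
| Fewer antigen-specific autoreactive T cells | Support | Support |
| More activated effector T cells | Not support (possible harm under 6.1.3) | Support |
| Shift in an unrelated circulating subset, equal in active and placebo | Not support | Support |
| Fewer autoreactive T cells, equal in active and placebo | Support | Support |
| Functional shift towards regulation, with number and phenotype unchanged | Support | Not support |

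Rows 2 and 3 are the defect that the SAP introduces. Row 4 is a gap in both documents. Row 5 is a case the SAP loses.

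**Step 3: what a shared drift does to a comparison with baseline.** This is an illustration. The drift sizes and the test are assumptions and are not in the documents. Let the drift be *d* standard deviations of the change score, the same in both arms, with no drug effect. For a within-arm two-sided 5% t-test against baseline, the noncentrality is *d*√n. Group sizes are n = 9 (one active cohort) and n = 4 × 9 = 36 (all active).

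| Drift *d* | *d*√9 | Chance of a change, n = 9 | *d*√36 | Chance of a change, n = 36 |
|---|---|---|---|---|
| 0 | 0 | 5% | 0 | 5% |
| 0.25 | 0.75 | 10% | 1.5 | 31% |
| 0.5 | 1.5 | 26% | 3.0 | 83% |
| 1.0 | 3.0 | 75% | 6.0 | above 99% |

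Against placebo, the expected contrast is (drift + drug effect) − drift = drug effect, so the shared part cancels. The comparison group exists: Protocol section 8 pools placebo across cohorts (4 × 3 = 12), and the Schedule of Assessments applies the same mechanistic sampling visits to all participants, including visits 0 and 14.

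**The case against.** The sentence is narrative text under an exploratory heading. It carries no test, threshold, marker list or decision, and the only listed secondary endpoint is the C-peptide AUC. The same SAP paragraph calls the product tolerizing and points to Protocol 2.2.2, which describes PPI-specific tolerance, so a sensible analyst would not read effector expansion as support. A supplement does not withdraw Protocol 8.4 or the monitoring in 6.1.3, and beta-cell harm is examined separately through the MMTT. Detail may also sit elsewhere: the protocol's abbreviation list includes a mechanistic analysis plan, and Protocol 10.2 mentions an immune biomarker plan.

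Much of this stands, and it limits the weight of the point. It does not remove the discrepancy. SAP 6.2 does not defer to either of those plans, and where it restates the criterion it leaves out exactly the words that carried the direction.

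Three stronger readings are tempting and are not supported:

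- *That nearly any immune data set would confirm the mechanism.* This needs a number of readouts, a test level and their dependence, none of which the documents give. It is also mainly a multiplicity argument. With no drift, a 5% test against placebo has the same error rate as a 5% test against baseline, so a placebo contrast alone would not answer it.
- *That the SAP removed a placebo comparison.* The sentence in Protocol 8.4 names no placebo comparator either, and measuring change from baseline does not exclude comparing that change between arms.
- *That every edit loosens the criterion.* Dropping function narrows it. The first-tier evidence is equally non-specific for tolerance in both documents.

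**Conclusion.** The discrepancy is real and rests on the text alone. SAP 6.2 replaces a directional, cell-specific criterion with one that has neither property, without explanation. Taken literally, it counts as support a finding that Protocol 6.1.3 treats as a possible harm, and it also counts drift shared with placebo.

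Its reach is modest. It concerns the second tier of evidence in an exploratory, descriptive analysis that serves a secondary objective. The primary safety endpoint, the first-tier evidence and the C-peptide analysis are untouched. The conclusion does not depend on the drift table, which only shows how a baseline-only reference behaves under assumed drifts of 0 to 1 SD. It does assume that no separate mechanistic plan, outside these documents, overrides SAP 6.2.

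**What to change.** In SAP 6.2:

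1. Restore the protocol's criterion: fewer antigen-specific autoreactive T cells, or a shift in their phenotype or function towards regulation. If the departure is intended, say so and give the reason. If a separate mechanistic plan governs, cite it.
2. State that expansion or activation of effector cells will be reported as a possible harm signal, in line with Protocol 6.1.3, and will not count as support.
3. As an improvement that neither document states for these measures, define the contrast as change from baseline to visit 14 in each dose cohort against the change in pooled placebo, and label other circulating-cell changes as descriptive.

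Items 1 and 2 align the SAP with the protocol; item 3 is new. The cost is SAP wording, with no new samples or assays, because placebo participants are already sampled on the same schedule. The downside is that fewer results can be called supportive. The change does not control multiplicity across readouts, so supportive findings should still be presented as exploratory.
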